### **Refractive Outcomes Evaluation of the VERION™ Image Guided System + ORA System with VerifEye**

Nowadays cataract patient's expectations are closer to those of refractive surgery patients. Patients want to be spectacle independent. However, fifteen to twenty percent of cataract surgery patients have from 1.00 to 3.00 diopters (D) of corneal astigmatism^1 which makes achieving spectacle independence unlikely in this patients unless the astigmatism is treated at the time of cataract surgery.

Currently available treatments include corneal or limbal incisions, the use of toric intraocular lenses (IOLs) or LASIK. Limbal relaxing incisions (LRIs) are the most commonly used manual method Traditionally, LRIs have been made manually (with a surgical knife). With the introduction of femtosecond laser to assist during cataract surgery, a new alternative is available for creating corneal incisions. The stability of the LRIs and visual outcomes using toric IOLs have been shown.

Regardless of the treatment of choice to correct the astigmatism at time of cataract extraction, a treatment plan has to be calculated preoperatively. This planning include: keratometry measurements and the use of a calculator to estimate the treatment and orientation of IOL and placement of the LRIs.

Keratometry can be measured using a variety of devices including manual keratometers (i.e. Javal-Shiotz), automated keratometers, corneal topography, and optical biometry ( IOL master and Lenstar).

Once keratometry to be used has been selected, if the treatment of choice are LRIs, a calculator is used to determine the location and size of the LRI. Many nomograms have been developed; the choice of nomogram is the surgeon's prefer one, usually based on prior experience, and their preferred knife. LRIs calculators are available on line. One frequently used is available at: <http://www.lricalculator.com/>. Accessed August 28, 2014. (Abbott Laboratories Inc. Abbott Park, Illinois, USA).A This calculator offers The Nichamin Age and Pachymetry Adjusted nomogram (NAPA), and the Donnenfeld Nomogram (DONO) that have been used to correct 0.75 to 3.75 D and 0.50 to 3.00 D of preoperative astigmatism respectively.2,4,5,6,A Both nomograms specify the location, length, size, and number of incisions based on the patient's age, the type of astigmatism, and the amount of astigmatism correction needed.2,4,6,A

If a toric IOL has been chosen then planning the appropriate orientation of the toric IOL is accomplished using an online software such as the Alcon Laboratories, Inc., AcrySof Toric IOL Calculation Online. Available at: <http://www.acrysoftoriccalculator.com/>. Accessed August 28, 2014).B The software selects the optimal AcrySof Toric IOL power and location based on the keratometry and the surgically induced astigmatism (SIA) values entered by the surgeon.

Intraoperatively, marking the eye and placing the incisions or aligning the toric IOL in the right axis are key steps for the success of astigmatism correction. Marking of the eye can be done using a variety of instruments using ink and it is routinely done with the patient in the upright position to avoid cyclorotation. Once patient is on the table in supine position, axis should be checked once again. Additional suggested methods to mark the eye include taking pictures preoperatively to identify anatomical landmarks similar to iris registration in refractive surgery. The use of iris registration during LASIK was introduced in 2008. Several publications have shown that patients undergoing wavefront-

guided LASIK with iris recognition achieved better visual and refractive outcomes compared to conventional LASIK.

Recently, Alcon introduced VERION™ Image Guided System: Digital Surgical Planning and Positioning Tools. This system encompasses a reference unit that takes a picture of the eye with the patient in the sitting position creating a high-resolution digital image of the patient's eye, capturing scleral vessels, limbus and iris features. It measures keratometry as well as the corneal diameter (limbus) and pupil size. The information captured is then transferred automatically to the planner where additional information including target refraction, manifest refraction, axial length, anterior chamber depth, and lens thickness is entered for IOL power calculation and astigmatism correction planning. Astigmatism correction options include corneal incisions, toric IOL and a combination of both. Intraoperatively, The VERION™ Digital Marker displays patient information and images from the VERION™ Reference Unit. Additionally it positions all incision locations and assists with lens alignment in real time while accounting for the variable impact of cyclorotation and patient eye movement. In the OR, it displays a reticle that helps to align the IOL to the axis according the surgical plan.c It also helps to position manual LRIs.

Additionally, intraoperative wavefront aberrometry has been used in the last couple of years with increase success. The Optiwave Refractive Analysis (ORA) system can refract the eye in phakic, aphakic, and pseudophakic states at any time during cataract surgery and assists in IOL power selection and recommendations for toric IOL positioning before and after implantation as well as LRIs confirming the surgery plan calculated preoperatively. Furthermore, VerifEye, an ORA hardware upgrade, provides continuous assessment of the patient's eye allowing for more precise measurements; therefore, more accurate results and improved refractive outcomes and VerifEye +, the latest upgrade that provides streaming information on the refractive status and correct IOL positioning through the right ocular of the surgical microscope. This enables the surgeon to visualize all the information without having to look up at the monitor screen during the surgical procedure.

This new technology is an alternative to plan and treat astigmatism at the time of cataract surgery. It could make this treatment easier for less experience surgeons by facilitating the calculations and making the identification of the correct axis easier by reducing the need for manual marks.

Our hypothesis is that if VERION™ Image Guided System: Digital Surgical Planning and Positioning Tools + ORA System with VerifEye or VerifEye + is used for measuring, planning and executing the astigmatism correction treatment at time of cataract surgery then refractive outcomes will be better.

## **OBJECTIVES:**

The main objective of this study is to evaluate spherical and astigmatism outcomes post routine cataract surgery when the complete VERION™ Image Guided System packet + ORA System with VerifEye or VerifEye + are used in the treatment of pre-existing astigmatism using toric intraocular lens (IOL) or corneal incisions compared to the surgeon's standard of care.

Exploratory objective is to evaluate the LRI enhancement feature of the ORA System with VerifEye or VerifEye + in subjects undergoing standard IOL implantation and corneal incisions.

### **STUDY DESIGN AND METHODS:**

1. **Test article:** The VERION™ Image Guided System: Digital Surgical Planning and Positioning Tools + ORA System with VerifEye or VerifEye +.
2. **Study Design:** Prospective, randomized, contralateral eye study.
3. **Subjects:**
  - a. **Inclusion Criteria:**  
Subjects MUST fulfill the following conditions to qualify for enrollment into the trial
    1. Subject is undergoing bilateral cataract extraction or refractive lens exchange with intraocular lens implantation and astigmatism correction.
    2. Gender: Males and Females.
    3. Age: 50 years and older.
    4. Willing and able to provide written informed consent for participation in the study
    5. Willing and able to comply with scheduled visits and other study procedures.

#### **b. Exclusion Criteria:**

Subjects with ANY of the following conditions on the eligibility exam may NOT be enrolled into the trial.

1. Severe preoperative ocular pathology: amblyopia, rubella cataract, proliferative diabetic retinopathy, shallow anterior chamber, macular edema, retinal detachment, aniridia or iris atrophy, uveitis, history of iritis, iris neovascularization, medically uncontrolled glaucoma, microphthalmos or macropthalmos, optic nerve atrophy, macular degeneration (with anticipated best postoperative visual acuity less than 20/30), advanced glaucomatous damage, etc.
2. Uncontrolled diabetes.
3. Use of any systemic or topical drug known to interfere with visual performance.
4. Contact lens use during the active treatment portion of the trial.
5. Any concurrent infectious/non infectious conjunctivitis, keratitis or uveitis.
6. Pseudoexfoliation syndrome or any other condition that has the potential to weaken the zonules
7. Previous refractive surgery.
8. Any clinically significant, serious or severe medical or psychiatric condition that may increase the risk associated with study participation or study device implantation or may interfere with the interpretation of study results.
9. Participation in (or current participation) any investigational drug or device trial within the previous 30 days prior to the start date of this trial.
10. Intraocular conventional surgery within the past three months or intraocular laser surgery within one month in the operated eye.

The principal investigator reserves the right to declare a patient ineligible or non-evaluable based on medical evidence that indicates the patient is unsuitable for the trial.

#### 4. Study Enrollment Procedures

Potential subjects will be identified from the patients presenting at the clinic. Additionally, an ad will be placed in the local newspaper and in the practice website. Once identified as a study candidate, the

patient will be asked if he/she would like to participate. The subinvestigator, study coordinator or an appropriately trained staff member will answer any and all questions and will obtain informed consent. A copy of the signed informed consent document will be given to the subject. The principal investigator will be available if the subject wants to discuss further details with him. Any testing that is part of the investigative site's standard preoperative cataract evaluation may be performed prior to the informed consent being signed, provided these tests are conducted within 90 days of surgery. The patient will understand that participation in the study, or declining to participate, will not affect his/her quality of care.

No subject will be enrolled into the study that does not meet the inclusion/exclusion criteria and does not sign the current approved informed consent document. Informed consent will be obtained prior to collecting any data for the study. The original signed documents will be maintained by the investigator as a permanent part of the subject's medical records. A signed copy will be provided to the subject.

## 5. Study Surgery Procedures

Eyes of the study participants will be randomly assigned to one of two groups:

- a. Group A, surgeon standard of care prior to getting VERION™ Image Guided System. Spherical power will be selected using the surgeon's preferred formula (Haigis, Holladay 2, Holladay, or other) and biometry method (IOL Master, Lenstar). Astigmatism correction will be planned using the surgeon's preferred keratometry method and calculator/nomogram to determine toric power and corneal incisions (i.e. Alcon toric calculator, Holladay toric calculator, AMO LRI calculator, etc). At time of surgery, axis of placement will be marked using blue ink marks. Corneal incisions will be made manually.
- b. Group B, VERION™ Image Guided System: Digital Surgical Planning and Positioning Tools + ORA System with VerifEye or VerifEye +. Spherical power of the IOL will be selected using the Verion™ Planner with the surgeon's preferred formula with an optimized A-constant (Haigis, Holladay 2, Holladay, or other). Both toric lenses and corneal incisions will be calculated with the Verion™ Planner using the Verion™ Reference Unit keratometry and white to white measurements, and Lenstar biometry. The VERION™ Digital Markers L and M will be used for axis of placement and confirmed using ORA System with VerifEye or VerifEye +.

## 6. Study Visit Schedule and Assessments (Table 1).

- a. **Visit Schedule:** Patients will be examined at the following intervals:

1. Visit 1: Screening and enrollment: Preoperative evaluation completed not more than eight weeks before surgery

2. Visit 2: Day of Surgery
3. Visit 3: Day 1 (12 to 48 hrs) after surgery
3. Visit 4: Month 1:  $30 \pm 10$  days postoperative after second eye surgery
4. Visit 5: Month 3:  $90 \pm 15$  days postoperative after second eye surgery

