**b. Measurements and evaluations**

1. Visit 1: Informed consent process will be conducted at this visit. Assessments include uncorrected and best-corrected ETDRS visual acuity (UCVA / BCVA), manifest refraction, intraocular pressure (IOP), and slit lamp examination including dilated fundus exam, auto refractor keratometry, Lenstar, VERION™ Reference Unit, and corneal topography (Atlas). Both IOL power and astigmatism correction will be calculated using the surgeon's current standard of care as well as using the VERION™ Image Guided System: Digital Surgical Planning. Any testing that is part of the site's standard of care preoperative cataract surgery evaluation may be performed prior to the informed consent being signed provided these tests are conducted within 90 days of the surgery and notation of the date performed is entered onto the source document.

The first eye undergoing surgery will be randomized to either one of the two groups: Group A (surgeon standard of care) or B (VERION™ Image Guided System + ORA System with VerifEye or VerifEye +). The fellow eye will be assigned to the alternate group. Eyes will be randomized after all calculations have been completed. Prior to randomization, all measurements, IOL power and astigmatism correction calculations will be reviewed following the practice standard of care to determine subject's eligibility for astigmatism correction with toric lens or corneal incisions. If it is determined that the measurements are not consistent then subject will be excluded from the study.

The surgeon's standard pre cataract surgery treatment will be used in all his patients.

2. Visit 2: The surgeon may use his preferred cataract extraction technique (manual or laser) for eyes randomized to Group A. Eyes randomized to Group B will undergo laser assisted phacoemulsification (primary incision, capsulorhexis and lens fragmentation) using the surgeon's preferred laser settings. The secondary incision will be made with the laser or manually, at the surgeon's discretion. The lens will be implanted in the bag. The surgeon's standard post cataract surgery treatment will be used in all his patients.
3. Visit 3: Assessment will include uncorrected ETDRS visual acuity, intraocular pressure, slit lamp examination, corneal incision location and/or toric IOL orientation.

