4. Visit 4 and 5: Assessment will include uncorrected and best-corrected ETDRS visual acuity (UCVA / BCVA), manifest refraction, auto refractor keratometry, Lenstar, VERION™ Reference Unit, corneal topography, intraocular pressure, and slit lamp examination. The location of all corneal incisions as well as toric IOL orientation will be documented.

Adverse events and device deficiencies/quality complaints will be monitored and recorded at all study visits.

**Table 1.** Visits and Study Assessments

Study Assessments	Visit 1 Preoperative	Visit 2 Operative	Visit 3 Day 1	Visit 4 Day 20-40	Visit 5 Day 75-105
Inclusion/Exclusion Criteria	x				
Consent Subject	x				
Patient demographics (age, gender, race, ethnicity)	x				
Manifest Refraction	x			x	x
UCDVA	x		x	x	x
BCDVA	x			x	x
Tonometry (IOP)	x		x	x	x
Complete slit lamp exam	x		x	x	x
Dilated fundus exam	x			†	†
Auto refractor keratometry	x			x	x
Atlas corneal topography	x			x	x
Lenstar LS900 measurements	x			x	x
Verion™ Reference Unit measurements	x			x	x
Verion™ Planner	x				
Alcon Toric calculator	x				
LRI calculator	x				
Incision Size and Location		x			
Record Lens Model Implanted (Attach label, or record manufacturer, model, power)		x			

VerifEye or VerifEye + information		x			
Post-IOL implantation incision size		x			
LenSx parameters		x			
Corneal arcs/toric IOL orientation		x	x	x	x
Adverse events / device deficiency	x	x	x	x	x

x To be performed as scheduled

† To be performed as deemed necessary by the investigator.

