**Primary Endpoint:**

- Residual refractive cylinder at 3 months

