**Secondary Endpoints:**

- Residual mean spherical equivalent refraction at 3 months
- Residual corneal astigmatism at 1 month and 3 months
- Residual refractive sphere at 1 month and 3 months
- Interim refractive cylinder at 1 month
- Percentage of eyes with postoperative MRSE accuracy to target  $\leq 0.5D$  at 1 and 3 months
- Uncorrected and best-corrected visual acuity at 1 month and 3 months
- Axis of placement (actual vs. intended)
- Lenstar K's vs. Verion K's
- Corneal incisions stability (manual vs. laser arcs) at 3 months after surgery - based on manifest cylinder and keratometry measurements from 1 and 3 months, noted above.

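### Visits 4 and 5 are timed only from the second eye's surgery, so the first eye of each pair is measured later than its 1-month and 3-month labels say

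*Combined protocol and SAP*

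**What the plan says.** The design is a "Prospective, randomized, contralateral eye study". Section 6.b states: "The first eye undergoing surgery will be randomized to either one of the two groups", and then: "The fellow eye will be assigned to the alternate group". Each subject therefore supplies one first-operated and one second-operated eye, in opposite groups.

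Section 6.a sets Visit 4 at 30 ± 10 and Visit 5 at 90 ± 15 "days postoperative after second eye surgery". Table 1 repeats the windows as "Visit 4 Day 20-40" and "Visit 5 Day 75-105" without saying which eye's surgery is day 0. It has a single operative column and a single Day 1 column.

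The primary endpoint is "Residual refractive cylinder at 3 months". Several secondary endpoints are set at 1 and 3 months. Incision stability (manual against laser arcs) is "based on manifest cylinder and keratometry measurements from 1 and 3 months". None of these is defined relative to the eye's own surgery.

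Same-day surgery is not required, and no minimum or maximum interval between surgeries is stated. Section 6.a asks for the preoperative evaluation within eight weeks of surgery, and section 6.b allows tests done before consent if they fall within 90 days of surgery; neither says which eye's surgery is meant. Statistical Considerations plans no adjustment for surgery order or time since surgery.

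**The concern.** In a contralateral-eye trial the comparison is made within the subject, so both eyes should be at the same stage of healing when they are compared. Under this schedule only the second eye is on the stated clock. The first eye is seen at the same visit but D days further from its own surgery.

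The stability endpoint is the most exposed, because it concerns change over healing time. The second eye contributes the change from about day 30 to day 90, and the first eye the change from about day D+30 to day D+90. If D is long, the early period in the first eye is not observed at all: Visit 3 includes neither refraction nor keratometry, so nothing usable for this endpoint is scheduled in that eye between its surgery and Visit 4. The 1-month endpoints have the same difficulty.

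**Working it through.** **Inputs.** Visit 4 at 30 ± 10 days and Visit 5 at 90 ± 15 days from the second surgery (section 6.a); Day 20-40 and Day 75-105 (Table 1). D is not in the documents, so it is treated as an assumption and shown over a range.

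**The plan's own windows.** 30 − 10 = 20 and 30 + 10 = 40; 90 − 15 = 75 and 90 + 15 = 105. Table 1 is reproduced when days are counted from the second surgery.

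**First-eye timing.** Days since the first eye's surgery = D + days since the second eye's surgery.

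| D (assumed) | First eye at Visit 4 | First eye at Visit 5 |
|---|---|---|
| 0 | 20-40 | 75-105 |
| 7 | 27-47 | 82-112 |
| 14 | 34-54 | 89-119 |
| 28 | 48-68 | 103-133 |
| 56 | 76-96 | 131-161 |

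At D = 56 the first eye's 1-month measurement lies entirely within days 75-105.

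**When one visit can suit both eyes.** For Visit 4, D + 20 ≤ 40, so D ≤ 20. For Visit 5, D + 75 ≤ 105, so D ≤ 30. At D = 14 the shared Visit 4 days are second-eye days 20 to 40 − 14 = 26, and the shared Visit 5 days are second-eye days 75 to 105 − 14 = 91.

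**Stability interval at nominal visit days.** Second eye: day 30 to 90. First eye: day 44 to 104 at D = 14, and day 86 to 146 at D = 56. The length is 60 days in both eyes; only its position in the healing course differs.

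**Shift between arms.** Assume 40 subjects (Sample Size gives 40 eyes per group but also mentions 20 subjects per group) and simple randomization (the method is not stated). The number of subjects with Group A first has SD √(40 × 0.25) = 3.16, so a 23/17 split is about one SD from even. The mean difference between arms in days since surgery is then (23 − 17)/40 × D = 0.15D: 2.1 days at D = 14 and 8.4 days at D = 56. Its expected value is zero.

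**The case against.** The strongest reply is that randomizing the first eye puts first and second eyes in both arms, so the delay cancels on average and the chance residue is small. That stands: both 2.1 and 8.4 days are well inside the ±15 days already accepted for Visit 5, and blocked randomization would shrink them further. It answers the question of bias, but it does not turn a day-76 reading into a 1-month reading or supply an early interval that was never observed.

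Second, the eight-week rule may limit D. A reader might infer that the delay is unbounded. If the rule covers both surgeries, D is capped at about 56 days; if it covers only the first, there is no cap. The text does not settle this, so the accurate statement is that no limit is explicit.

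Third, a reader might infer that late first eyes breach the visit windows. They do not: section 6.a counts those windows from the second surgery, and a first eye seen at D + 90 days complies.

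Fourth, nothing in the documents shows that cylinder changes materially between day 90 and, say, day 104 or day 146, and the introduction says that the stability of limbal relaxing incisions has been shown. First eyes are measured later, never earlier, so every in-window Visit 5 follows at least 75 days of healing. This stands for the primary endpoint. For the same reason it cannot be asserted that instability is understated in first eyes, since no healing curve is given.

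Finally, stability is one secondary endpoint, relevant only to eyes with corneal incisions and analysed only if the primary endpoint is significant. That limits the weight of the point but does not remove it.

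**Conclusion.** The point holds in a limited form. A trial that follows the plan exactly measures every first eye D days later than its fellow eye and reports both under the same label. With same-day surgery the offset vanishes, and with a gap of about a week many first-eye visits still fall in days 20-40 and 75-105. Beyond 20 days no in-window Visit 4, and beyond 30 days no in-window Visit 5, can meet those ranges for the first eye.

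The consequence is within-pair noise, some chance imbalance between arms (0.15D days at a 23/17 split of an assumed 40 subjects), and mislabelling that matters mainly for the 1-month and incision-stability endpoints. The documents do not support a claim that one arm is favoured or that the 3-month primary comparison is invalid. The size depends on D, which they do not give. The change is worth making because it is cheap and because missing early measurements cannot be recovered later.

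**What to change.** 1. In section 6.a and Table 1, define the Visit 4 and Visit 5 windows from each eye's own surgery.
2. Where the windows overlap (D up to 20 days for Visit 4, up to 30 days for Visit 5), book the joint visit on a day inside both.
3. Record days since surgery for each eye at each visit.
4. Include surgery order or days since surgery as a term in the paired analyses of the 1-month, 3-month and stability endpoints. Keep all pairs in the main analysis and give an in-window-only analysis as a sensitivity check.

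Treatment and sample size do not change. The cost is tighter booking (at D = 14 the joint Visit 4 must fall on second-eye days 20-26; at D = 20 only day 20 is left) and one extra model term. Where the windows do not overlap, the first eye's value is kept with its true timing recorded. The model can allow for that timing but cannot supply a 1-month value that was not measured. A separate first-eye visit would supply it, but at the price of an extra attendance and of losing same-session measurement of the pair, and is not needed for the main comparison.
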